PI	Principal Investigator
SADE:	Serious Adverse Device Effect
SAE:	Serious Adverse Events
UADE:	Unanticipated Adverse Device Event

PROTOCOL SUMMARY

Study Title:	A Multicenter Observational Study to Evaluate Outcomes of EmboCube Gelatin Embolization to Control Bleeding or Hemorrhage
Study Objective:	To collect clinical safety and performance outcome data associated with the use of EmboCube Embolization Gelatin to control bleeding or hemorrhage.
Study Device:	EmboCube Embolization Gelatin
Study Design:	Multicenter observational post-market clinical follow-up study in subjects treated with EmboCube
Device Regulatory Status:	CE mark approved March 2019 (CE 667862).
Sample size:	
A minimum of 100 subjects will be included. This sample size is based on a one-sample non-inferiority analysis of Clinical Success based on the parameters listed below and a 15% loss-to-follow-up:
 
 • Reference Clinical Success rate (p_0): 92% • Treatment rate (p): 90% • Non-inferiority margin: 10% • α: 0.05 • Power: 80% 
The reference Clinical Success rate is based on historical clinical literature data for benchmark gelatin embolic devices.

Subject Population:	Subjects who are treated with EmboCube to control bleeding or hemorrhage in accordance with the current approved CE Mark indication for use as stated in the Instructions for Use (IFU).
Clinical Sites:	Up to 7 centers may be included to allow enrollment of required subjects.
Study Follow-Up:	Data will be collected to 28 days post procedure.
Estimated Study Duration:	
First patient enrolled: July 2022
 
Last patient enrolled: July 2023
 
Last patient, last visit: August 2023

Primary Endpoints:	
The primary performance endpoint will be clinical success defined as cessation of bleeding post-embolization and absence of rebleeding at the treated site requiring reintervention (repeat embolization or additional surgery) within 24 hours.
 
The primary safety endpoint will be absence of unanticipated serious adverse device effects within 24 hours.

Secondary Endpoints:	
 1. Incidence of adverse events (serious and device and/or procedure-related) to 24 hours post-operative. 2. Incidence of adverse events (serious and device- and/or procedure-related) between 24 hours and 28 days post-operative. 3. Technical success defined as successful occlusion of the target area as seen on post-embolization angiography. 4. Incidence of device observations relating to EmboCube.
Inclusion Criteria:	
 1. Age \geq18 years 2. Subject requires embolization and is suitable for treatment with EmboCube in accordance with device Instructions For Use for the treatment of bleeding or hemorrhage.

	
 3. Subject provides written informed consent to study data collection. 4. The subject has Social Security (applicable only in France)
Exclusion Criteria:	
 1. Bleeding site in the neck, head, or brain. 2. Subject has co-morbidity with survival prognosis of less than 30 days, in the opinion of the treating physician. 3. In the investigator's opinion, participation in the study may not be in the subject's best interest. 4. Pregnant woman, person under guardianship or curatorship, persons under judicial protection, and persons who do not write or speak French (applicable in France only). 
Refer to the EmboCube Embolization Gelatin IFU for a complete list of device contraindications.

1 INTRODUCTION AND BACKGROUND

1.1 Introduction

This is a multicenter, observational study of the use of EmboCube Embolization Gelatin to control hemorrhaging and bleeding. The study is designed to enable the collection, analysis and reporting of data from “real-world” use of EmboCube used in accordance with the Instructions for Use (IFU) associated with the product’s CE Mark approval.

Data collection will include that relating to safety and effectiveness and the period of observation during which data will be collected will extend from the index procedure through 28 days post procedure. Data collection will be according to the standard follow-up practice of the enrolling institution.

1.2 Literature Summary

Gelatin based embolics are among the earliest materials utilized for therapeutic arterial embolization. Due to absorbability, this material is the preferred device when shorter occlusion time is the objective, a permanent implantable is not desired, or distal super selective targeting is not the goal. A principal use of resorbable embolic material is the management of hemorrhage from spontaneous conditions, instrumentation, or trauma. In each of these uses the goal typically is to achieve an immediate plugging of the source of blood loss without causing permanent ischemia. A large number of publications of case studies and cohort evaluations of comparable gelatin embolics demonstrate clinical success rates of 80-100% (depending on condition) in the control of acute bleeding and massive hemorrhage.

The indication of control of hemorrhaging and bleeding and pre-operative embolization covers a wide range of causes (trauma, postpartum, instrumentation, idiopathic, etc.) in a variety of anatomical locations (limbs, uterus/reproductive tract, viscera, etc.), and in populations ranging from healthy to those with multiple comorbidities or polytrauma. Frequently the bleeding occurs in an emergency situation, requiring rapid medical response and treatment. Although comparable resorbable gelatin embolics have been used to stop bleeding and hemorrhaging and for pre-operative embolization for decades, EmboCube is a more recent product.

1.3 Alternative Treatments / Interventions

There are a number of different hemostatic agent classes and respective methods utilized to mitigate bleeding or hemorrhage. The class and agent(s) a physician chooses are influenced by multiple factors, including how rapidly the bleeding can be controlled, location and type of wound, preference of the medical professional treating the patient, etc.

On a more systemic scale, mechanical agents used to control bleeding and hemorrhage include clamps, tourniquets, sutures, etc. However, for control of acute bleeding and hemorrhage (including intravascular use) temporary mechanical hemostatic agents, like EmboCube Embolization Gelatin are frequently selected. These agents work to obstruct the bleeding site and function temporarily as a scaffold to accelerate the formation of a blood clot and return to homeostasis. Gelatin, collagen, and oxidized regenerated cellulose are three materials that constitute the majority of mechanical agents. (Chiara 2018)

1.4 Device Description

EmboCube Embolization Gelatin consists of biocompatible, hydrophilic, and dry pre-cut cubes of resorbable porcine gelatin packaged in a 10-mL syringe with a standard luer lock tip. Where approved, EmboCube Embolization Gelatin is sold in two sizes (2.5 mm and 5.0 mm) and three weight configurations. Each sterile syringe is intended for single patient use only.

A full description of the device can be found in the Instructions for Use (IFU).

1.5 Study Purpose

The study is designed to enable the collection, analysis, reporting and presentation of data from use of EmboCube in accordance with the Instructions for Use associated with the product’s CE Mark approval.

The intent of this study is to increase the understanding of the performance of EmboCube in 'real world' patient population, encompassing a broad spectrum of causes of bleeding, treated areas, and patient profiles, to confirm the product's performance and safety in general clinical practice. The intended use of EmboCube includes high-risk anatomical sites and conditions, and so the data collected will be used to amplify knowledge about known or estimated risks, clinical and technical performance, and to identify and evaluate any potential unanticipated adverse device effects, and to integrate that information into product risk analysis and update the clinical evaluation report and labeling, if appropriate.

2 STUDY DEVICE

2.1 Intended Use

EmboCube Embolization Gelatin will be used in accordance with the current approved CE Mark indication for use as stated in the Instructions for Use (IFU):

EmboCube Embolization Gelatin is indicated for use in embolization of blood vessels to occlude blood flow to control bleeding/hemorrhaging in the peripheral vasculature.

2.2 Device Regulatory Status

CE Mark was approved March 13, 2019, by BSI (CE 667862).

2.3 Device Preparation and Use

EmboCube Embolization Gelatin will be prepared and used as described in the IFU that accompanies each device.

Procedures for patient treatment and follow-up, including medication, will be according to hospital / institutional standard of care and physician medical judgement.

3 STUDY PLAN

3.1 Study Objective

To collect clinical safety and performance outcome data associated with the use of EmboCube Embolization Gelatin to control bleeding or hemorrhage.

3.2 Design

Multicenter, observational, post-market clinical follow-up study in subjects treated with EmboCube.

This study does not involve submitting subjects to any procedures additional to those performed under normal conditions of use of the device.

3.3 Enrollment

A minimum of 100 subjects undergoing embolization with EmboCube for the treatment of bleeding or hemorrhage will be enrolled in the study. The study will be conducted at up to 7 centers globally.

3.4 Study Population

Subjects undergoing embolization with EmboCube for the treatment of bleeding or hemorrhage who meet the inclusion and exclusion criteria are intended to participate in this study. The eligibility criteria are kept to a minimum to better represent the subject profile treated in actual clinical practice without selecting sub-groups of particular low/high risk or excluding certain diseases or anatomies.

3.5 Study Duration and Follow-Up

It is anticipated that enrollment will commence in July 2022 and is expected to continue until July 2023. The last subject visit is expected in August 2023.

Subject follow up visits will be in accordance with standard of care. Data will be collected from available

medical records for baseline (medical history), index hospitalization, up to 24 hours post procedure, and until 28 days post-procedure. If there is no routine clinic visit or follow-up between 4- and 6-weeks post procedure (28 days +14 days), subjects will be contacted by telephone during this time to collect safety follow-up to 28 days.

Start of study is defined as the date of initiation (authorization to start enrollment) of the first site.

Completion of the study is defined as the completion of the last follow-up visit/contact for the last subject.

4 ENDPOINTS AND SUBJECT POPULATION

4.1 Primary Outcome Measures

4.1.1 Primary effectiveness endpoint

The primary performance endpoint will be clinical success defined as cessation of bleeding post-embolization and absence of rebleeding at the treated site requiring reintervention (repeat embolization or additional surgery), within 24 hours.

4.1.2 Primary safety endpoint

The primary safety endpoint will be absence of unanticipated serious adverse device effects within 24 hours.

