7.4 Adverse Event Reporting Requirements

7.4.1 General Reporting Requirements

Reportable adverse events should be recorded on the eCRF through 28 days post index-procedure.

The report should include: the description of event, severity, duration, action taken, treatment outcome and relationship of the adverse experience to the study device and/or procedure (refer to section 12 for definitions for causality and severity).

All reportable events should be followed until resolution, or study exit.

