8 RISK/BENEFIT ASSESSMENT

8.1 Risks

EmboCube Embolization Gelatin is being used in accordance with the approved CE Mark indication and Instructions for Use.

Vascular embolization is a high-risk procedure. Complications may occur at any time during or after the procedure, and may include, but are not limited to, the following as listed in the device IFU:

- Stroke or cerebral infarction
- Occlusion of vessels in healthy territories
- Vascular rupture
- Neurological deficits
- Infection or hematoma at the injection site
- Allergic reaction, cutaneous irritations
- Transient pain and fever
- Vasospasm
- Death
- Ischemia at an undesirable location, including ischemic stroke, ischemic infarction (including myocardial infarction), and tissue necrosis
- Blindness, hearing loss, loss of smell, and/or paralysis

There are no interactions with concomitant medical treatments identified in the device IFU.

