9.2 Primary Endpoint Analysis

Endpoints will be analyzed using the intention-to-treat analysis set. An additional supportive analysis will be conducted in the PP analysis sets for the primary safety and effectiveness endpoints. All available data will be used for each endpoint and no imputations will be done.

The primary endpoint of clinical success will be presented as frequency and percentage.

The primary safety endpoint of absence of SADE within 24 hours, will be presented as frequency and percentage.

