7.1.2 PRIMARY SAFETY ENDPOINT

The primary safety endpoint will be the absence of unanticipated serious adverse device effects within 24 hours.

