8.2 PRIMARY DATA ANALYSES

Endpoints will be analyzed using the ITT analysis set. Additional supportive analyses will be conducted in the PP analysis sets for the primary safety and effectiveness endpoints. All available data will be used for each endpoint and no imputations of data are planned.

The primary endpoint of clinical success (defined as cessation of bleeding post-embolization and absence of re-bleeding at the treated site requiring re-intervention [i.e., repeat embolization or additional surgery], within 24 hours) will be presented as frequency and percentage.

Endpoint Derivation:

- “Was there a re-intervention to treat bleeding?” is checked NO, **AND**
- “Was occlusion of the treated area (as seen on post-embolization angiogram) successful?” is checked YES, **AND**
- “Did subject have any re-interventions post-procedure through 24 hours post-procedure?” is checked NO

The primary safety endpoint of absence of serious adverse device effect within 24 hours will be presented as frequency and percentage

Endpoint Derivation:

- “Did any serious and device- and/or procedure-related adverse events occur during the procedure or up to 24 hours post-procedure?” is checked NO

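### The primary safety endpoint is defined and titled as absence of unanticipated serious device effects, but the SAP computes something broader, and aligning to the written definition would leave a largely uninformative endpoint

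*Protocol*

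**What the plan says.** The endpoint appears in three forms.

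- **Unanticipated SADE.** Protocol 4.1.2: "The primary safety endpoint will be absence of unanticipated serious adverse device effects within 24 hours". SAP 7.1.2: "The primary safety endpoint will be the absence of unanticipated serious adverse device effects within 24 hours". The protocol summary, the SAP synopsis and both primary-endpoint table titles in SAP 9.1 (ITT and PP) carry the same restriction.
- **Any SADE.** Protocol 9.2: "The primary safety endpoint of absence of SADE within 24 hours, will be presented as frequency and percentage". SAP 8.2, in its text: "The primary safety endpoint of absence of serious adverse device effect within 24 hours will be presented as frequency and percentage".
- **Any serious device- or procedure-related event.** The derivation beneath that text in SAP 8.2 counts a success when one question is answered no: "Did any serious and device- and/or procedure-related adverse events occur during the procedure or up to 24 hours post-procedure".

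Protocol 7.1 defines AE, ADE, SAE, SADE and procedure-related AE, but no unanticipated category; UADE appears only in the abbreviations. The only list of complications is in Protocol 8.1. It says that complications "may include, but are not limited to, the following as listed in the device IFU", and the bullets include death, stroke, vascular rupture, myocardial infarction, tissue necrosis and paralysis. Protocol 7.4.1 sets the content of an event report: "The report should include: the description of event, severity, duration, action taken, treatment outcome and relationship of the adverse experience" to the device or procedure. Anticipated status is not among the items, nor is it in the SAP 8.4 listing.

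**The concern.** A primary endpoint should have one definition, and the rule that produces the number should implement it. Here the definition and table titles say one thing, the analysis text a second and the derivation a third. A reader of the results table would take the percentage as freedom from unanticipated device effects, when it is freedom from any serious device- or procedure-related event. A serious event caused only by the procedure would count against the device.

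The direction in which the conflict is settled also matters. The obvious tidy-up is to bring the derivation into line with the definition. That would make the result depend on a classification that the documents neither define nor record. If the 8.1 list became the reference, few serious device effects could fail the endpoint. Protocol 1.5 says that "the data collected will be used to amplify knowledge about known or estimated risks", and a primary safety result that excludes known risks by construction would contribute little to that.

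**Working it through.** The documents give no target rate, margin or sample size for safety; the 100 subjects were sized on clinical success. There is therefore no planned safety figure to reproduce. The check applies each written version to the same cases.

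| Case, within 24 h | V1: no unanticipated SADE (Protocol 4.1.2, SAP 7.1.2, SAP 9.1 titles) | V2: no SADE (Protocol 9.2, SAP 8.2 text) | V3: question answered no (SAP 8.2 derivation) |
|---|---|---|---|
| Serious device-related event of a type in 8.1, including death | Success, if 8.1 is the reference | Failure | Failure |
| Serious device-related event not in 8.1 | Failure, unless the open-ended wording is read to cover it | Failure | Failure |
| Serious event related only to the procedure | Success | Success | Failure |
| No serious related event | Success | Success | Success |

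**Ordering.** An unanticipated SADE is a SADE, and a SADE is a serious device-related event. A subject who fails V1 therefore fails V2, and one who fails V2 fails V3, provided the site's yes/no answer agrees with its event forms. Hence the success percentage satisfies V1 ≥ V2 ≥ V3.

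**Illustration.** The event counts are assumed; the documents give none. Take n = 100. SAP 8.1 specifies Clopper-Pearson exact 95% intervals for categorical endpoints. With s successes:

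- lower limit = 2.5% quantile of Beta(s, n − s + 1)
- upper limit = 97.5% quantile of Beta(s + 1, n − s), or 1 if s = n

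Suppose 3 subjects have a SADE of a listed type and 2 other subjects have a procedure-only serious event, with 8.1 taken as the reference for V1:

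- V1: 100/100 = 100.0% (96.4 to 100); the lower limit is 0.025^(1/100) = 0.964
- V2: (100 − 3)/100 = 97.0% (91.5 to 99.4)
- V3: (100 − 3 − 2)/100 = 95.0% (88.7 to 98.4)

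Suppose instead that 5 subjects have listed SADEs and none has a procedure-only event. V1 stays at 100.0% (96.4 to 100), while V2 and V3 both give 95.0% (88.7 to 98.4). Under that reading V1 does not respond to listed events however many occur.

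**The case against.** The strongest reply is that the SAP derivation, not the definition, produces the number, and it has no filter for anticipated status. This stands. A reader might infer from Protocol 4.1.2 and the 8.1 list that a device-caused death within 24 hours would be reported as a safety success. The documents do not support that for the planned analysis: such a death fails under Protocol 9.2 and under the SAP 8.2 derivation. Nor would it be hidden, since Protocol 7.2 requires all deaths to be reported as SAEs whatever their cause.

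Four further points limit the concern.

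- No section calls the 8.1 list the reference for anticipated status. Protocol 7 speaks of comparing events with anticipated event rates, which may imply a different basis. The statement that V1 would be uninformative is therefore conditional.
- The eCRF, the IFU, the adjudicator's charter and the separate safety plan are not in the documents. One can say only that no field for anticipated status is described.
- Protocol 1.5 also names the detection of unanticipated effects as a purpose, so reporting them is legitimate. A named subset does that.
- Known risks are covered elsewhere, by the secondary endpoints and the SAP 8.4 safety summary. The cover from the secondary endpoints is partial, because SAP 8.3 counts only events judged definitely related. SAP 8.4 has no such limit.

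None of this removes the mismatch between the definition, the table titles and the derivation.

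**Conclusion.** The inconsistency is certain from the text and should be corrected before analysis. One primary endpoint has three versions that differ in two ways: whether anticipated device effects count, and whether procedure-only events count. As the plan stands, the derivation is the strictest version, so the reported percentage would be no more favourable than the label implies. The fault is that the figure does not measure what its title says and mixes procedure events into a device endpoint.

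The size is unknown, because no event rates are given. In the assumed example, 3 listed SADEs and 2 procedure-only events in 100 subjects separate the versions by up to 5 percentage points (100%, 97% and 95%).

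That settling the conflict on the written definition would leave a largely uninformative endpoint is a conditional conclusion. It rests on 8.1, or something like it, serving as the reference list, and on no closed definition existing outside these documents.

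**What to change.** 1. Define the primary safety endpoint as absence of any SADE within 24 hours, anticipated or not, in the protocol summary, Protocol 4.1.2, the SAP synopsis and SAP 7.1.2. Protocol 9.2 and the SAP 8.2 text already say this.
2. Replace the SAP 8.2 derivation with one built from serious events having a device relationship, and state which causality categories of Protocol section 12 count as related. Report serious procedure-only events separately. Changing the definition without the derivation would leave the two in conflict.
3. Retitle the two primary-endpoint tables in SAP 9.1.
4. Report unanticipated SADEs as a named subset. Give a definition, a fixed closed reference list and a named classifier, who could be the independent adjudicator of Protocol 10.17. Record the status in one field before results are tabulated.

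The cost is wording in both documents and one data item; serious device-related events are already collected. The safety percentage may be less favourable than under the unanticipated definition. It would be no lower than under the current derivation if the same events and relationship categories are counted, since procedure-only events would no longer fail a subject.

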4.2 Secondary Endpoints

1. Incidence of adverse events (serious and device- and/or procedure-related) to 24 hours post-operative.
2. Incidence of adverse events (serious and device- and/or procedure-related) between 24 hours and 28 days post-operative.
3. Technical success defined as successful occlusion of the treated site as seen on post-embolization angiography.
4. Incidence of device observations relating to EmboCube.

4.3 Eligibility Criteria

Subjects are required to meet ALL the following criteria in order to be included in this study:

4.3.1 Inclusion Criteria

1. Age ≥ 18 years
2. Subject requires embolization and is suitable for treatment with EmboCube in accordance with device Instructions For Use for the treatment of bleeding or hemorrhage.
3. Subject provides written informed consent to study data collection.
4. The subject has Social Security (applicable only in France)

